5.4.2 Selection of the Placebo Control

This study will compare each of the three moxidectin doses to placebo to establish background Complete Cure rates in the absence of clear untreated control data for the disease. The placebo arm will provide data on the natural course of scabies, which has been poorly defined in the literature, and address subjective elements of symptomology. Several therapies are approved and available for scabies treatment, but data supporting their use are highly variable in quality and consistency: published meta-analyses of historical scabies research has reproducibly found randomized controlled trials have greatly differed in design and execution^{12,21,22}, with design issues including the absence of blinding or random treatment allocation, and lack of consistency in the definition of the primary endpoint. The uncertainty in the “true” effectiveness of any potential active control poses a significant challenge when designing a comparative study, even when the treatments have been shown to be efficacious in clinical practice. Therefore, a placebo control was selected for this study because active control effect size estimates are not well-supported by the results of historical scabies randomized controlled trials. There is no increased risk to patients of temporary deferral of treatment as long as active pruritus management is undertaken and household contacts are treated. The placebo control presents the most statistically robust method to confirm moxidectin’s efficacy.

A conservative estimate of the placebo control cure rate has been proposed by basing this on the two recently completed Phase 3 Natroba® (spinosad) trials which used a topical vehicle control²³. A meta-analysis of the vehicle control cure rates from these studies, calculated using the non-responder imputation for scabicide exposure, results in a 40% Day 28 Complete Cure rate for placebo. This hypothetical Complete Cure rate is considered conservative as the topical vehicle control contained benzyl alcohol, an ingredient that may have activity against the scabies mite.

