4 SAMPLE SIZE DETERMINATION

Approximately 200 index subjects will be randomized into one of four cohorts using an equal allocation ratio. Only one subject will be enrolled per household; where more than one household member is screened for the study, the index subject is the youngest eligible member of the household.

The target sample sizes per randomized treatment group are shown in [Table 2](#). The sample size was selected to address the study's primary efficacy objective.

Table 2: Sample Size by Randomized Treatment Group

Randomized Treatment Group	Target Sample Size
Placebo	N = 50
Moxidectin 8 mg, single dose	N = 50
Moxidectin 16 mg, single dose	N = 50
Moxidectin 32 mg, single dose	N = 50

A sample size of 50 subjects per randomized treatment group will yield an approximate power of 75% for the pairwise comparisons of each moxidectin dose group to placebo assuming a placebo Day 28 Complete Cure rate of 40% or less and a moxidectin Day 28 Complete Cure rate of 70% or more. Power calculations for each pairwise comparison were conducted via a Z test for two independent proportions with pooled variance at a two-tailed adjusted alpha of 0.019. The pairwise adjusted alpha of 0.019 is used to control the familywise error rate (FWER) at an overall two-tailed alpha of 0.05 using a large sample approximation to Dunnett's critical value for the 3 pairwise comparisons of each moxidectin dose group to placebo.

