6 STUDY ENDPOINTS

6.1 Primary Efficacy Endpoint

The primary efficacy endpoint is the proportion of index subjects achieving Complete Cure at Day 28. Complete Cure is defined as demonstration of both:

(1) Clinical cure (all signs and symptoms have completely resolved, including burrows, inflammatory/noninflammatory lesions and pruritus).

and

(2) Microscopic or dermatoscopic cure demonstrating the absence of mites, eggs, and/or scybala, and negative dermoscopy for burrows.

Complete Cure will be derived from the individual assessments captured on the Day 28 Scabies Assessment eCRF page where:

- Lesion count is 0, and,
- Pruritus is ‘Absent’, and,
- Mites are ‘Absent’, and,
- Eggs are ‘Absent’, and,
- Scybala are ‘Absent’, and,
- Burrows (by dermoscopy) are ‘Absent’.

An index subject will be considered as having achieved Complete Cure at Day 28 if all of the 6 components are either 0 or “Absent” as specified above. If any of the 6 components are missing, whether because the individual component is missed or because the Day 28 visit was missed, the Complete Cure endpoint at Day 28 will be considered missing and the subject will be imputed as a non-responder (not cured). An exception will be made if the missed visit is non-informative. See Section 9.11.2 for further detail on handling missing data for the Day 28 Complete Cure endpoint.

The Day 28 Complete Cure endpoint for subjects exposed to scabicides prior to their Day 28 assessment will also be imputed as a non-responder (not cured). Scabicides are defined as any scabicide, including permethrin, ivermectin, benzyl benzoate, sulfur, lindane, crotamiton, malathion, tea tree oil, or spinosad used between Day 0 and Day 28. Scabicides do not include products used to manage the symptoms of scabies. Subjects exposed to scabicides as concomitant medications with unknown start dates will also be imputed as non-responders, unless the end date is known and after Day 28.

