12 APPENDICES

Appendix 1: Fixed Imputation for Non-Informative Missing Day 28 Complete Cure Endpoints

For subjects missing a Day 28 Complete Cure endpoint because of non-informative reasons, their endpoint will be imputed as a non-responder or responder using a logistic regression. The process will follow the following steps:

1. Run a logistic regression model using FAS subjects with non-missing Day 28 responses. This will include those subjects whose Day 28 response was imputed because of informative missing data.
2. Using the coefficients from the logistic regression, calculate the probability of achieving a Day 28 Complete Cure for those subjects with missing outcomes due to non-informative missing.
3. If the predicted probability for the subjects with non-informative missing is > 0.50 then impute a responder/cured status for their Day 28 Complete Cure endpoint.
4. If the predicted probability for the subjects with non-informative missing is ≤ 0.50 then impute a non-responder/not cured status for their Day 28 Complete Cure endpoint.

The logistic model will include demographic and baseline covariates and is pre-specified to include randomized treatment group as listed below. Should the logistic regression fail to converge, or produce unreliable coefficients/SEs because of multicollinearity or other reasons, a backward stepwise selection of covariates for removal will be conducted until the logistic model converges. The backward stepwise model will begin by using a significance level for removal of 0.10. If the model still does not converge the significance level for removal will be set to 0.05. Randomized treatment group will be a "locked" covariate and not eligible for removal. If the logistic regression model still fails after attempts at backward elimination, the observed proportions of Complete Cure responders in each randomized treatment group will be calculated across all regions and including any "informative" imputations, but excluding the non-informative missing data subjects. For the non-informative missing data subjects, if the observed proportion for their randomized treatment group is > 0.50 they will be imputed as achieving Complete Cure at Day 28. If the observed proportion for their randomized treatment group is ≤ 0.50 they will be imputed as not achieving Complete Cure at Day 28.

Logistic Regression Model Covariates:

- Region
- Randomized Treatment Group
- Age
- Gender
- BMI
- Race (collapse or eliminate if too sparse)

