Appendix 2: Non-Informative Missing - Multiple Imputation for Complete Cure

As described in Section 9.11.2, if the percent of FAS participants whose Day 28 Complete Cure (ComC) outcome is missing due to non-informative reasons exceeds 5%, the ComC outcome for these subjects will be imputed using multiple imputation (MI) for the primary efficacy analysis. The implementation of the MI will proceed according to the steps outlined below. The MI process described here also includes the individual treatment group point estimates of the ComC and the three exploratory pairwise comparisons comparing each moxidectin dose group to the other moxidectin dose groups.

All of the MI datasets, as well as the bootstrapped sampled datasets, will be available. Complete documentation of the seed(s) and program code for the imputation, bootstrap and final derivation of the MI estimators will be such that the imputed and bootstrapped datasets may be replicated. Should the imputation model fail to converge, produce unreliable SEs, or irrational imputations, the imputation for non-informative missing subjects will default to the methods outlined in Appendix 1.

Step 1: Derivation of the MI FAS Dataset

Define the MI FAS dataset as FAS subjects with an observed Day 28 ComC or a non-informative missing Day 28 ComC. Leave the missing Day 28 ComC for non-informative missing subjects as missing. For the MI FAS dataset, include subjects exposed to scabicides prior to Day 28 whether their Day 28 endpoint is observed or not and set their ComC to Not Cured. Exclude any subject missing a Day 28 ComC that is considered “informative” missing.

Step 2: Definition of the Imputation Model

Define the imputation model imputing the Day 28 ComC outcome, to be a logistic regression with the following covariates:

- Region
- Age
- Gender
- BMI
- Race (collapse or eliminate if too sparse)
- Previous history of scabies
- Number of lesions
- Evidence of burrows
- Evidence of pruritus
- Number of regions affected

If the model does not converge or fails, stepwise backward elimination will be implemented, similar to that outlined in [Appendix 1](#).

Step 3: Generate M=50 Multiple Imputed Datasets

- Using the MI FAS data set in Step 1 and the imputation model in Step 2 above, generate 50 multiple imputed datasets stratified by randomized treatment group i.e. multiple imputed independently for each randomized treatment group (200 datasets total). Should

CONFIDENTIAL

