the imputation model fail to converge or produce unreliable SEs, or irrational imputations for any of the randomized treatment groups, the imputation for non-informative missing subjects will default to the methods outlined in [Appendix 1](#) and no further attempts at MI will be made. If the imputation model is successful in generating the MI datasets continue with the remaining MI Steps.

- For each of the 50 imputation runs, append the 4 randomized group datasets together forming a single MI dataset that contains the data for all four treatment groups resulting in 50 datasets.
- Subjects with missing ComC due to “informative” reasons, and initially excluded from the MI FAS dataset, will now be added to each of the 50 MI datasets with their missing ComC outcome set to Not Cured for each of the 50 datasets.
- Refer to these M=50 datasets as the Final MI datasets.

Step 4: Derive the MI Estimator for the Average Predicted Probability for each Treatment Group and the Risk Difference for Each Pairwise Comparison (Substantive Model)

For each of the Final 50 MI datasets from Step 3 above, each of which now contains all FAS subjects, calculate the Average Predicted Probabilities for each randomized treatment group and the Risk Difference for all six pairwise comparisons using the methods outlined in [Section 9.11.1](#). The six pairwise comparisons include the three primary analysis pairwise comparisons of each moxidectin dose group to placebo and the three pairwise comparisons of each moxidectin dose group to the other moxidectin dose groups.

Step 5: Derive the Bootstrapped SEs for the MI Estimator of the Group Average Predicted Probabilities and the Pairwise Risk Differences

For each of the Final 50 MI datasets using the methods outlined in step 3, generate B=1000 bootstrapped samples (with replacement) to calculate the SEs for the Average Predicted Probabilities and the Risk Differences calculated in Step 4.

Step 6: Use Rubin’s Rule to Derive the MI Estimators and SEs

Using Rubin’s Rule ([Carpenter, J.R. and Kenward, M.G. 2013](#)) generate the MI estimators and their variances/SEs for the Average Predicted Probabilities for each randomized treatment group and the Risk Difference for all six pairwise comparisons across the 50 MI datasets calculated in Step 5.

Step 7: Calculate p-values and 95% CI for the MI Estimators

- **Primary Efficacy Analysis: Pairwise Comparison of each Moxidectin Group to Placebo**

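### The multiple-imputation model is fitted with scabicide users coded Not Cured but fills in only recorded non-users, so imputed cure probabilities are too low in any arm with scabicide use

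*SAP*

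**What the plan says.** - **Outcome rule.** SAP 6.1 says the Day 28 endpoint "for subjects exposed to scabicides prior to their Day 28 assessment will also be imputed as a non-responder". SAP 9.11.2 repeats this, and has rescue use settled before the Day 42 blind break.
- **Multiple imputation (SAP Appendix 2).** Step 1 builds the fitting dataset and says to "include subjects exposed to scabicides prior to Day 28 whether their Day 28 endpoint is observed or not", with the outcome set to Not Cured. The same step leaves out subjects whose outcome is missing for informative reasons. Step 2 lists ten covariates: region, demographics, history and baseline disease. None records scabicide use. Step 3 fits the model separately in each arm. The informative-missing subjects, "initially excluded from the MI FAS dataset, will now be added to each of the 50 MI datasets", then return as Not Cured.
- **Fixed imputation (SAP Appendix 1).** This applies when non-informative missingness is 5% or less, or if multiple imputation fails. Step 1 reads "Run a logistic regression model using FAS subjects with non-missing Day 28 responses", and adds that informative-missing subjects already set to non-response are included. Scabicide users are not named. They carry a non-response value under 6.1 and nothing removes them, so their presence is an inference. A predicted probability above 0.50 becomes cured, otherwise not cured.
- **Tipping point (SAP 9.11.3.2).** Values imputed for non-informative missingness stay unchanged throughout.

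**The concern.** Informative-missing subjects and scabicide users have the same status: a rule, not a model, makes them Not Cured. Appendix 2 removes the first group before fitting and keeps the second, without giving a reason. With the users in, the model estimates the probability of being cured and not having used a scabicide. It then applies that to people already recorded as non-users, who need the probability of cure given no use. The second is higher wherever the arm has any users.

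At stake is a bias in the primary risk difference whose sign depends on how scabicide use splits between arms. Bootstrap and Rubin standard errors do not reflect it, and the tipping-point analysis does not vary these values.

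**Working it through.** **Inputs from the documents.** SAP section 4 gives 50 subjects per arm, a Z test for "two independent proportions with pooled variance at a two-tailed adjusted alpha of 0.019", power of about 75%, and rates "assuming a placebo Day 28 Complete Cure rate of 40% or less and a moxidectin Day 28 Complete Cure rate of 70% or more". Protocol 5.4.2 derives the placebo figure from vehicle arms, "calculated using the non-responder imputation for scabicide exposure, results in a 40% Day 28 Complete Cure rate for placebo". The 40% therefore already counts users as failures.

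**Inputs that are assumptions.** Neither document gives a scabicide-use rate by arm or an expected non-informative missing rate. I take use of 5 to 30% on placebo and 3 to 20% on moxidectin, with 5 to 15% of each arm imputed.

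**The plan's own figure.** The pooled null SE is √(2 × 0.55 × 0.45/50) = 0.0995. The alternative SE is √(0.40 × 0.60/50 + 0.70 × 0.30/50) = 0.0949. With z = 2.3455, power = Φ[(0.30 − 2.3455 × 0.0995)/0.0949] = 75.9%, which agrees with the stated figure.

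**Formula.** In one arm, let p be the cure rate with users counted as Not Cured, r the share of users and m the share imputed. Subscripts c and t denote placebo and moxidectin.

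- A non-user is cured with probability p/(1 − r), but the model with users in it targets about p.
- Shortfall per imputed subject = p/(1 − r) − p = p·r/(1 − r).
- Effect on the risk difference ≈ m × [pc·rc/(1 − rc) − pt·rt/(1 − rt)].

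This assumes the same m in both arms and missingness unrelated to outcome among non-users. Because missing non-users leave the fitting set while users stay, the exact value is this divided by (1 − m).

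**Sign.** The effect favours moxidectin only if rc/(1 − rc) > (0.70/0.40) × rt/(1 − rt), that is, placebo odds of use above 1.75 times moxidectin odds. Placebo use must exceed 8.4% when moxidectin use is 5%, 16.3% when it is 10%, and 30.4% when it is 20%.

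**Size at 40% versus 70%** (approximate formula; positive favours moxidectin):

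| Use, placebo / moxidectin | Shortfall, placebo | Shortfall, moxidectin | m = 5%, points | m = 10%, points |
|---|---|---|---|---|
| 5 / 5% | 0.021 | 0.037 | −0.08 | −0.16 |
| 10 / 10% | 0.044 | 0.078 | −0.17 | −0.33 |
| 20 / 20% | 0.100 | 0.175 | −0.38 | −0.75 |
| 10 / 5% | 0.044 | 0.037 | +0.04 | +0.08 |
| 20 / 10% | 0.100 | 0.078 | +0.11 | +0.22 |
| 20 / 5% | 0.100 | 0.037 | +0.32 | +0.63 |
| 30 / 5% | 0.171 | 0.037 | +0.67 | +1.35 |

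Two exact values:

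- m = 8%, use 20/4%: 0.08 × (0.100 − 0.0292)/0.92 = +0.62 points.
- m = 15%, use 30/3%: 0.15 × (0.1714 − 0.0216)/0.85 = +2.64 points.

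For scale, the planned difference is 30 points with SE 9.5.

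**Simulation check.** A large-sample simulation used one covariate that predicts both scabicide use and cure, with 10% of non-users missing (so fewer than 10% of an arm is imputed). The multiple-imputation bias was +0.32 points at 20/5% use, +0.74 at 30/5% and −0.67 at 20/20%. Fitted on non-users only, it was within 0.04 points of zero in every scenario.

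**Appendix 1.** A lower probability matters only if it crosses 0.50. Without covariates, the placebo non-user rate 0.40/(1 − r) passes 0.50 only when r > 20%, and moxidectin stays above 0.50 either way. In the same simulation with 6% of non-users missing, close to this branch's 5% limit, the risk difference was inflated by 1.1 to 2.0 points; 0.6 to 1.8 points remained with users excluded. At 10% missing the figures were 1.8 to 3.3 and 1.0 to 3.2. A large part of that branch's bias therefore comes from the cut-off, which is a separate matter.

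**The case against.** Four arguments on the other side carry weight.

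- **Size.** The larger figures need heavy missingness and heavy, unequal scabicide use together. The plan works against both: scabicides are prohibited before Day 28 (Protocol 11.2.3), subjects with intolerable itch should not be enrolled (Protocol 8.5.2), and undocumented reasons for missing data default to informative (SAP 9.6). This stands and limits the point.
- **Recorded non-users only.** If use up to Day 28 is unknown for someone who missed the visit, an arm-level rate that includes users is defensible for that person. This stands for such subjects. It does not explain why users stay in when use has been ascertained.
- **Simplified checks.** The formula has no covariates and the simulation has one, while the SAP model has ten. Baseline covariates that predict scabicide use could change the size. They cannot replace conditioning on use itself.
- **Other analyses.** The Complete Analysis Set contains no imputed subjects. It also drops scabicide users, so it answers a different question and does not check this step.

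A reader might go further and infer that the plan inflates the moxidectin effect. The documents do not support that. More rescue on placebo is the natural expectation if moxidectin works, but no rates are given, and at equal use the bias runs against moxidectin.

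A reader might also infer a raised false-positive rate. If moxidectin did nothing, a blinded randomised trial would expect equal cure and equal use across arms, and the formula then gives zero. A raised rate needs equal overall cure with unequal use. With 50% cure in all arms and use of 25% versus 5%, cure among non-users would be 0.50/0.75 = 67% on placebo and 0.50/0.95 = 53% on moxidectin, an artificial pattern.

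**Conclusion.** The point holds in a limited form. Appendix 2 targets the wrong conditional probability for recorded non-users, and its imputed cure probabilities are too low in any arm with scabicide use. The direction of the effect on the risk difference is not known in advance. Under the assumed rates it is usually under 1 point either way. It passes 1 point at about 30% placebo use, 5% moxidectin use and 10% imputed, and reaches about 2.5 points only with about 15% imputed and 30% placebo use. All of these rest on assumed use and missingness rates and on the planned 40% and 70%.

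For Appendix 1 the same feature is an inference from the text, and it changes a result only where a prediction crosses 0.50. This is a small defect in the primary analysis, worth correcting because the remedy is already in the SAP.

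**What to change.** Before the Day 42 blind break:

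- **Appendix 2 Step 1:** exclude subjects with recorded pre-Day 28 scabicide use from the MI FAS dataset. **Step 3:** add them back to each of the 50 datasets as Not Cured, alongside the informative-missing subjects.
- **Appendix 1 step 1, and its observed-proportion fallback:** fit on subjects with an observed Day 28 outcome and no recorded scabicide use. This also leaves out informative-missing subjects, which matches Appendix 2.
- State that all these subjects remain Not Cured in the primary analysis.

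The cost is a few sentences of SAP text and fewer subjects for fitting. For example, at 70% cure and 10% use, a moxidectin arm of 50 keeps 35 cured but falls from 15 to 10 not cured, before missing subjects are removed. With ten covariates this makes the existing backward-elimination and fallback steps somewhat more likely to be needed. The change does not address the 0.50 cut-off in Appendix 1.

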8.2 Inclusion Criteria

A subject must meet all the following inclusion criteria:

1. Aged 18 years or older.
2. Provided written informed consent.
3. Diagnosis of active scabies infestation confirmed by the presence of clinical signs and symptoms (evidence of burrows or typical inflammatory/noninflammatory lesions and pruritus) and either microscopic confirmation of scabies mite(s), ova or scybala by skin scraping or dermoscopy.
4. All female subjects of childbearing potential must agree to the use of a highly effective method of birth control until 16 weeks after administration of IP (Section 8.4.1).

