1.2 Changes to Protocol Planned Analyses

The following changes have been made to the planned analyses described in the clinical study protocol MDGH-MOX-2002 Version 3 dated 28 Dec 2023:

- The description of the process for randomization, described under Section 10.1 of the current study protocol, was updated in this SAP Section 5.1. Instead of a unique screening number, a site specific sequential Subject Number was allocated to each subject who provided written informed consent. This Subject Number was used throughout the study to identify the subject. A unique Randomization Number was assigned to the subject upon randomization and this randomization number was only recorded on the Randomization electronic case report form (eCRF) page. Study drug was dispensed according to the Randomization Number, not according to the Subject Number.
- Two additional sensitivity analyses have been included to support the primary efficacy analysis:
 - A Completers Analysis excluding subjects with missing data for the primary endpoint with the exception of subjects exposed to scabicides.
 - An analysis that adjusts for Baseline lesion count as the sole covariate, other than randomized treatment group.
- The protocol states that sensitivity analyses will be conducted to assess the impact of missing data on the results. As such, a tipping point analysis has been included in the SAP.
- A repeat of the primary analysis within each Region will not be conducted due to anticipated small sample size within one of the Regions. However, descriptive analyses of the primary efficacy endpoint stratified by Region will be provided.

- Exploratory pairwise comparisons between each of the moxidectin dose groups have been added.
- For the non-informative missing data, the Complete Cure endpoint may be imputed via a fixed value using the methodology detailed in [Appendix 1](#). Should the missing data due to non-informative reasons be 5% of the total sample size, (approximately 200 subjects), a multiple imputation (MI) approach will be implemented using the methodology detailed in [Appendix 2](#).
- The following additional exploratory endpoints have been included in this SAP that are not otherwise listed in the current study protocol:
 - The Day 28 Complete Cure without regards to pruritus.
 - The proportion of index subjects achieving clearance for each individual component of the Complete Cure endpoint

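### Above 5% non-informative missingness, ten-covariate imputation models are fitted arm by arm in about 46-47 subjects, and one arm failing on undefined criteria moves the primary analysis to deterministic imputation

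*SAP*

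**What the plan says.** SAP 9.11.2 and Table 1 reserve MI for non-informative missingness above 5% of the sample; at or below that, Appendix 1 single imputation applies. (SAP 1.2 words the threshold as 5%, not above 5%.)

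Appendix 2 then works as follows.

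- Step 2 lists ten covariates: region, age, gender, BMI, race, previous scabies, number of lesions, burrows, pruritus and number of regions affected.
- Step 3 fits this model arm by arm: "generate 50 multiple imputed datasets stratified by randomized treatment group i.e. multiple imputed independently for each randomized treatment group".
- Step 2 gives one failure rule: "If the model does not converge or fails, stepwise backward elimination will be implemented, similar to that outlined in" Appendix 1, which removes covariates at 0.10 and then 0.05.
- The introduction and Step 3 give another: failure leads to Appendix 1. In Step 3 the trigger is "the imputation model fail to converge or produce unreliable SEs, or irrational imputations for any of the randomized treatment groups", after which MI is not tried again.

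Appendix 1 sets a missing outcome to cured if the predicted probability exceeds 0.50 and to not cured otherwise.

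Two of the covariates may be sparse. SAP 1.2 drops the within-region repeat of the primary analysis "due to anticipated small sample size within one of the Regions", and Protocol 8.2 makes itch part of the diagnosis at entry: "evidence of burrows or typical inflammatory/noninflammatory lesions and pruritus".

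**The concern.** Ten covariates are too many for a logistic model in one arm of this trial, so at least one of the four fits may well fail. The text does not say plainly what follows. Step 2 reduces the model; the introduction and Step 3 go to Appendix 1 without mentioning that reduction. The terms for unreliable standard errors and irrational imputations have no definition, so two statisticians could choose different primary methods from the same blinded data.

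The destination matters as much as the switch. A 0.50 cut pushes each arm towards its majority outcome. Appendix 3 completes all imputation before the bootstrap, so the filled-in values are then treated as observed. This would happen in the branch with the most missing data.

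**Working it through.** **1. Planning figure.** SAP section 4 states: "A sample size of 50 subjects per randomized treatment group will yield an approximate power of 75% for the pairwise comparisons", "assuming a placebo Day 28 Complete Cure rate of 40% or less and a moxidectin Day 28 Complete Cure rate of 70% or more", by a "Z test for two independent proportions with pooled variance at a two-tailed adjusted alpha of 0.019". With pooled p = 0.55, the null SE is √(2 × 0.55 × 0.45/50) = 0.0995, the alternative SE is √((0.24 + 0.21)/50) = 0.0949, and z = 2.346. Power = Φ[(0.30 − 2.346 × 0.0995)/0.0949] = 0.759. The stated 75% is reproduced, so 50 per arm and 40%/70% are the right inputs.

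**2. Arm size.** More than 5% of 200 means at least 11 missing, or 2.75 per arm, which leaves about 47 observed. At 8% missing (16 subjects), 46 remain.

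**3. Events per covariate** = n × min(p, 1 − p)/10.

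| Observed per arm | Placebo (40%) | Moxidectin (70%) |
|---|---|---|
| 46 | 18.4/10 = 1.8 | 13.8/10 = 1.4 |
| 48 | 19.2/10 = 1.9 | 14.4/10 = 1.4 |

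For comparison, a pooled model on 4 × 46 subjects has 27.6 + 3 × 13.8 = 69 not cured. With three treatment terms, region and log lesion count, that is 69/5 = 13.8 per term.

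**4. Separation of the full model in at least one arm.** This was simulated at 40/70/70/70% with a linear-programming check. The documents give no covariate prevalences, so all of them are assumptions.

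| Assumed covariates | Full model | After Step 2 elimination |
|---|---|---|
| Fairly balanced | about 17-19% | 0-1% |
| Smaller region 20%, pruritus 90%, burrows 85% | 82-84% | 0-1% |
| Smaller region 10%, pruritus 97%, burrows 90%, race 3 levels | about 100% | 0-1% |

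A second simulation gave 42% with regions split 50/50 and pruritus and race dropped. Broadly, the full model is separated in 10-40% of trials with balanced covariates and 80-100% with a sparse region or near-universal pruritus. Elimination kept a median of 8-9 covariates in the arms that first failed.

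**5. After elimination.** Removing separation does not make the fit stable. With 46 per arm and 200 trials per scenario, at least one arm still had a log-odds SE above 1.5 in 47% of trials (fairly balanced), 82% (region 20%, pruritus 90%) and 93% (region 10%, pruritus 95%). An SE of 1.5 gives a 95% interval for the odds ratio spanning exp(2 × 1.96 × 1.5) ≈ 358-fold. The 1.5 cut-off is an assumption, because the SAP gives none.

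**6. Effect of the fallback.** Let m be the missing fraction, equal in all arms and completely at random. If every missing subject takes the majority outcome of the arm, the bias is

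[0.7(1 − m) + m] − 0.4(1 − m) − 0.3 = 0.70m.

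- 11 missing (m = 0.055): 3.9 points.
- 16 missing (m = 0.08): 5.6 points.

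This is an upper limit, since covariates move some predictions across 0.50. Simulating Appendix 1 at 8% missing gave a 32 mg versus placebo difference of 0.33 with non-prognostic covariates and about 0.316 with prognostic lesion count, against a true 0.30. The bias is therefore +1.6 to +3 points.

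The direction depends on the arms lying on opposite sides of 0.50. At 20% and 40%, for example, all missing subjects become not cured and the bias is 0.4(1 − m) − 0.2(1 − m) − 0.2 = −0.2m.

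**7. Detection.** SAP 9.11.3.2 holds non-informative imputations fixed in every tipping-point iteration. The Complete Analysis Set (SAP 8.5) removes these subjects, but also scabicide users and informative missing outcomes, so it does not isolate the effect.

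**The case against.** The best defence is that the steps form a sequence. Step 3 uses the model from Step 2, and Step 2 includes elimination, so the Appendix 1 default is naturally read as a last resort. On that reading separation alone would seldom trigger it (0-1% of simulated trials). This stands. A reader might infer from the full-model figures that separation is the expected result and that MI would hardly ever be used. The documents do not support that: they prescribe elimination, and they give no prevalences from which to fix the probability.

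A reader might also infer that the fallback breaks a protocol commitment to MI. It does not. Protocol 15.6.2 and 15.6.8 announce alternatives in case MI proves unreliable, and SAP 1.2 and Table 1 declare the fixed imputation.

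The bias is also modest: 1.6 to 3 points is about 0.2 to 0.3 of the 9.5-point SE of the risk difference. It arises only above 5% non-informative missingness, and undocumented reasons default to informative (SAP 9.6). Imputed subjects will be listed (SAP 9.11.2). All of this limits the size of the point.

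The defence does not answer three things: the undefined criteria, the one-arm trigger, and the choice of a deterministic cut when a random draw would serve. The SAP sees the overfitting risk elsewhere: section 9.11.4.2 leaves region out of a model on the whole FAS to limit covariates.

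**Conclusion.** The point holds, conditional on more than 5% non-informative missingness. The arm-specific models are overfitted on the plan's own figures (1.4 to 1.9 events per covariate). The order of the failure rules is not explicit, two triggers are undefined, and one arm can switch the primary method for all four. The fault lies in the form of the fallback; having one is legitimate.

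If the fallback is used at the planning rates with 8% missing, the risk difference is inflated by about 1.6 to 3 points, with a ceiling of 0.70m, and imputation uncertainty is left out of the SE. These sizes assume 40%/70% cure, equal missingness across arms and missingness completely at random. The separation and SE figures also rest on assumed covariate prevalences. How often the fallback would be used cannot be stated, because the criteria are open.

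**What to change.** In Appendix 2:

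1. Replace the four arm-specific models with one imputation model on all arms, containing randomized treatment, region and log baseline lesion count, fitted with a penalised or augmented likelihood. Keep M = 50 and Rubin's rules.
2. State one ordered failure rule with defined criteria. Reduce covariates first, always keep treatment, and keep region as long as possible because the primary model adjusts for it.
3. As a last resort, draw each missing outcome at random from the posterior cure probability of its arm, within MI.
4. Delete the default to the Appendix 1 cut from the introduction and Step 3.

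The cost is SAP wording and a small program change before the Day 42 blind break. The downside is an assumption of common covariate effects across arms, which Appendix 1 already makes. In simulation a pooled model of this kind showed no bias, though lesion count was both the prognostic factor and a model term there.
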